Treatment of Perianal Fistulas in Crohn's Disease with Injection of Freshly Harvested Autologous Adipose Tissue: A placebocontrolled and randomized study

Participants

Department of Hepatology and Gastroenterology, Aarhus University Hospital

Ph.d [name]

[name], MD

Ph.d [name]

Department of Surgery, Pelvic Floor Unit, Aarhus University Hospital, Aarhus

Ph.d [name]

[name] [name]

Gastrounit, Herlev Hospital

Ph.D [name]

[name]

Department of Abdominal Surgery, Odense University Hospital

[name], MD

Surgical Department, Køge Hospital

Ph.d [name]

Abdominalcenter K, Bispebjerg Hospital

[name]

Aim

To investigate the effects of injection of freshly harvested autologous adipose tissue in 140 patients with Crohn's Disease (CD) and complex perianal fistulas.

Primary endpoint

Number of patients who have achieve complete clinical healing 6 months after treatment with freshly harvested adipose tissue. Complete clinical healing is defined as i) if the patient has no symptoms of discharge; (ii) no visible external fistula opening in the perineum; (iii) no internal opening can be palpated with rectal digital examination (iv) no signs of a fluid conducting tract at the location of the former fistula.

Secondary endpoints

- a) Number of patients who have achieve complete clinical healing 3 months after treatment with freshly harvested adipose tissue.
- b) Number of patients with complete or partial healing 6 months after treatment.
- c) Reduction of symptoms evaluated by the Perianal Disease Activity Index (PDAI) 3 months after treatment.
- d) Reduction of symptoms evaluated by the Perianal Disease Activity Index (PDAI) 6 months after treatment.
- e) Changes in fecal inconsistency evaluated by St. Marks score

Background

Perianal fistulas are frequently present in Crohn's Disease (CD). The cumulative incidence of CD patients who develop perianal fistulas is as high as 26% during 20 years of follow-up, with the greatest risk present in the first 10 years after diagnosis.

Treatment of perianal fistulas with cultured mesenchymal stem cells derived from adipose tissue marrow has shown efficacy in CD patients. The use of cultured autologous cells, however, has the disadvantage of being time consuming, as it involves a harvesting procedure and weeks of *in vitro* stem cell expansion.

The injection of freshly harvested autologous adipose tissue is an easily accessible alternative to *in vitro* expanded autologous adipose-derived stem cells.

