Present study investigate the effects of injection of freshly harvested autologous adipose tissue in 140 CD patients with complex fistulas.

Methods

Design

The study is a randomized double-blinded and placebo-controlled interventional study. It will be conducted as a national multicenter study. Based on a power-calculation 140 patients will be included. An interim analysis will be performed after the inclusion of 80 patients.

Patients

Inclusion Criteria

- a) Diagnosed with Crohn's Disease
- b) Perianal fistula with out branching or cavities with one external and one internal opening, which due to the risk for development of incontinence is not suitable for lay-open procedure, meaning: 1) all anterior interspinchteric and low transspinchteric (involving<1/3 of spinchter) in women 2) high interspinchteric fistulas 3) high

transsphincteric (>1/3 of sphincter), suprasphincteric and ekstrasphincteric fistulas 4) intersphincteric or low transsphincteric fistula in patients with fecal incontinence and/or fecal urge.

- c) no or minimal luminal disease activity by colonoscopy < 3 months before treatment defined by Simple Endoscopic Severity for Crohn's Disease<3
- d) Prior optimal medical treatment for fistulas (immunmodulators, antibiotics and/or anti-TNF-alfa treatment) with out achieving fistula healing
- e) Treatment with seton for a minimum of 6 weeks
- f) Speaks and understand Danish

Exclusion Criteria

- a) Pregnancy
- b) Changes in immunmodulator or anti-TNFalfa treatment < 12 weeks
- c) Anovaginal fistulas
- d) Rectal or anal stenosis
- e) Active proctitis
- f) Stoma
- g) Previous surgery for fistulas besides simpel drainage or seton
- h) Smoker
- i) Insulin-dependent diabetes, conditions inducing defective immunity, previous pelvic radiation
- j) pelvic MRI contraindicated

Study course

Included patients will in the period before treatment with freshly collected adipose tissue or placebo receive standard surgical (regular curettage and seton) and/or medical treatment for their fistula(s). When the treating surgeon estimates (reduced secretion and fistula shrinkage) that the patients can achieve fistula healing by injection with freshly collected adipose tissue patients will be referred to pelvic MRI for exact fistula classification. The patient will only be included if pelvic MRI confirms that the fistula is applicable for treatment with freshly collected adipose tissue.

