Data analysis will be performed as intention-to-treat. A power-calculation has shown a power of 80 % based on the assumptions that 55% of the patients receiving active treatment and 30 % of the patients receiving placebo achieves clinical healing 6 months after treatment with a level of 0.05 for significance, when including 60 patients in each group. We have chosen to include a total of 140 patients who will be randomized 1:1. An interim analysis will be performed after 80 included patients. In case this interim analysis demonstrates a clear and statistical significant effect of the treatment compared to placebo further inclusion in the study be terminated.

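### The efficacy stop at 80 patients has no numeric boundary and the final test no adjusted level, so the 0.05 level is not held (about 8% if both looks are tested at 0.05)

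*Combined protocol and SAP*

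**What the plan says.** The statistical plan is one paragraph, under Statistical considerations. It reports 80% power for healing rates of 55% and 30%, "with a level of 0.05 for significance, when including 60 patients in each group", and then sets the total at 140, randomised 1:1. It goes on: "An interim analysis will be performed after 80 included patients". Recruitment ends if that analysis "demonstrates a clear and statistical significant effect of the treatment compared to placebo further inclusion in the study be terminated".

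The Design section mentions the same look, "An interim analysis will be performed after the inclusion of 80 patients", and adds no rule. The primary endpoint is "Number of patients who have achieve complete clinical healing 6 months after treatment with freshly harvested adipose tissue".

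The documents give no interim p-value or Z boundary, no spending function, no final level other than 0.05 and no named test. They do not define a clear effect or say whether only benefit can stop the trial.

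**The concern.** The primary comparison gets two chances to succeed, at 80 patients and at 140, and the plan supplies one level calculated for a single look. If 0.05 is used each time, the overall false-positive rate exceeds 0.05. If a stricter interim threshold is intended, it is not written down, so no reader can confirm that it was fixed before the data were seen.

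Timing adds a second gap. The look is triggered by inclusions, but the endpoint is read 6 months after treatment. If the analysis is done when the 80th patient enters, the most recent patients have no primary outcome, and the share of information at the interim is unknown.

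At stake is the credibility of a positive result. An early stop at 80 would be the most exposed, because it could be challenged as the product of an unadjusted extra look.

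**Working it through.** **Inputs.** From Statistical considerations: level 0.05, power 80%, healing 55% vs 30%, 60 per group in the power calculation, 140 in total at 1:1 (70 per group), interim at 80 (40 per group). Assumed: two-sided testing, and 6-month outcomes on all 80 at the interim unless stated otherwise.

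**Step 1: reproduce the plan's figure.** With pooled rate 0.425 and n = 60 per group:

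power = Φ{[0.25√60 − 1.96√(2 × 0.425 × 0.575)] / √(0.55 × 0.45 + 0.30 × 0.70)} = Φ{(1.9365 − 1.3703) / 0.6764} = Φ(0.837) = 79.9%.

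This matches the stated 80%. The two-sided sample-size formula gives 61 per group and the one-sided formula 48, so the calculation is two-sided, uncorrected and for one look. Exact power at 60 per arm is 80.6% for the uncorrected chi-square test and 75.0% for Fisher or Yates.

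**Step 2: error with 0.05 at both looks.** Under no effect, the two test statistics are bivariate normal with correlation √(80/140) = 0.756. Then

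P(|Z1| ≥ 1.96 or |Z2| ≥ 1.96) = 0.05 + 0.05 − P(both) = 0.10 − 0.0194 = 0.0806.

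False claims of benefit are half of this, 4.03% instead of 2.5%. Exact binomial enumeration (40 then 70 per arm, common healing rate 20% to 50%, uncorrected chi-square) gives 7.97% to 8.69%. A single look at 70 per arm gives 4.85% to 5.16%.

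**Step 3: vary what the plan leaves open.** The final test is at 0.05 throughout.

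| Reading | Overall type I error |
|---|---|
| p<0.05 at both looks, uncorrected chi-square | 8.06% (exact 8.0% to 8.7%) |
| Same, stop only for benefit, two-sided final test | 6.5% (exact 6.4% to 6.9%) |
| Interim p<0.01 | 5.4% |
| Interim p<0.005 | 5.1% |
| Interim p<0.001 | 5.01% |
| p<0.05 at both, Fisher | 4.9% to 5.5% (single look 3.1% to 3.4%) |
| p<0.05 at both, Yates | 4.3% to 5.5% (single look 2.9% to 3.4%) |
| p<0.05 at both, 60 evaluable at interim | 8.5% |
| p<0.05 at both, 40 evaluable at interim | 9.0% |

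**Step 4: boundaries that hold 0.05 at 80 of 140 (t = 0.571).**

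- O'Brien-Fleming-type spending, 0.05 spent two-sided: interim 2[1 − Φ(1.96/√t)] = 0.0095, final 0.0463.
- The same with 0.025 spent per side: interim 2 × 2[1 − Φ(2.2414/√t)] = 0.0061, final 0.0481.
- Haybittle-Peto: interim 0.001, final 0.0499 (computed 0.04986).

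Each pair gives 5.00% by normal approximation. Exact errors with the uncorrected chi-square are 4.9% to 5.5%, 4.9% to 5.3% and 4.9% to 5.2% respectively; the excess over 5% comes from discreteness.

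**Step 5: power and chance of stopping, exact, 55% vs 30%, 70 per arm.**

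| Rule | Power | Chance of stopping at 80 |
|---|---|---|
| 0.05 at both looks | 87.4% | 64% |
| 0.0095 then 0.0463 | 85.8% | 37% |
| 0.0061 then 0.0481 | 85.7% | 30% |
| 0.001 then 0.0499 | 85.6% | 15% |
| Single look at 140 | 85.6% | none |

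**The case against.** The strongest reply is that 8% is near the top of the range. The rule asks for an effect that is both clear and significant, which suggests something stricter than p<0.05, and an effect of treatment compared with placebo reads most naturally as benefit. Benefit-only stopping gives 6.5%, and a strict interim threshold gives 5.4% or less. The analysis test is also unnamed: a power formula need not reveal it, and Fisher at both looks would give roughly the nominal level.

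That is fair as to size. The 8% is conditional, and the match between the power figure and an uncorrected test is only indirect evidence of the test intended. But the reply does not supply the missing rule. An undefined qualifier cannot be checked, and even p<0.01 followed by an unadjusted 0.05 exceeds 5%. Fisher stays near 5% only because its conservatism absorbs the extra look, which still adds about two points to its single-look error.

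Two further points stand as limits. The plan stops further inclusion; it does not say that the interim p-value is the trial's result. If patients already enrolled but not yet at 6 months were added to the final claim, the error would differ from these figures, and that case was not modelled. Nor do the documents say when the open choices will be made, only that they are not stated.

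**Conclusion.** The concern holds. The plan permits an efficacy stop on the primary endpoint with no numeric boundary and no adjusted final level, so following it as written does not hold the stated 0.05.

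The type I error is about 8% if both looks use an uncorrected chi-square test at two-sided p<0.05, stopping can go either way, all 80 have 6-month outcomes, and the interim result stands as the trial's result. Across the other readings in the table it runs from 4.3% to 9.0%. The lower values depend on a strict threshold or a conservative test that the plan does not specify.

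This must be fixed before the interim analysis. It bears on the error rate of the primary claim and cannot be credibly repaired once the interim data have been seen.

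**What to change.** Replace the qualitative stopping wording with a pre-specified numeric group-sequential boundary that keeps the overall two-sided error at 0.05. In the same paragraph:

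- name the test used at both looks;
- say whether stopping is for benefit only;
- trigger the interim by the number of patients with 6-month outcomes, not by inclusions;
- say how patients enrolled but not yet at 6 months enter the final analysis after an early stop.

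Any pre-specified rule of this kind will do; the three pairs in step 4 are examples for 80 evaluable patients. Recompute if the interim falls elsewhere: with 60 evaluable, the first O'Brien-Fleming-type pair becomes p<0.0028 then p<0.0489. If a strict exact bound at 5% is wanted, allow for the small excess from discreteness shown there.

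The cost is one paragraph and no extra patients. Power stays at 85.6% to 85.8%, level with a single look at 140. The real downside is a lower chance of stopping at 80 under the planned effect: 37%, 30% or 15% instead of 64%. Waiting for 80 patients with 6-month outcomes also delays the look, so more patients may be enrolled before any stop.
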